- 1) Visually display a driver's license or state ID

- 2) Visually display an alternative photo ID (employee ID, school ID, etc) in combination with a piece of mail displaying the subject's name.
- 3) Visually display an alternative photo ID (employee ID, school ID, etc) alone
- 4) Visually display one of the following pieces of mail with subject's name and address: utility bill, cellphone bill, correspondence from the secretary of state or other government organization
- 5) Visually displaying any piece of mail listing the subject's name and address
- 6) Asking the subject to verbally state their name

2. **Day 1 Survey.** Following consent, study participants will complete an electronic survey that includes social network inventory. Identifying information of social network members (first name and last initial and cross streets/zipcode/neighborhood) is collected through self-report for the purposes of connecting social networks of study subjects. Day 1 Survey is found in Appendix B. This will survey will be completed on the day of recruitment and will take 60 minutes. The RA can interview participants who have difficulty self-administering the survey.
3. **Randomization.** Will occur following the survey, and participants in the SNS+messaging arm will receive the messaging intervention (discussion tools and coaching). Study participants will be randomized to receive no messaging (i.e., SNS only) or SNS+messaging with equal probability. Randomization will be performed at the participant level, meaning that in general, participants within a recruitment cluster will be assigned to different groups. Random assignments will be provided by the University of Chicago via a web-based API, with the touchpads programmed to retrieve an assignment at the appropriate time and deliver the messaging (or not), as appropriate.

Indexes and first-degree referrals will be randomized as described above. Second-degree referrals will also be randomized, however, we will not ask for additional SNS referrals from them if the study sample size has been reached.

4. **Messaging Intervention.** Study staff will be notified of group allocation and provide the in-person message reinforcement and will address questions related to messaging.

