Other Important Variables: Age, race, ethnicity, gender, sex at birth, and CJI history; as well as COVID-19 knowledge, testing history, infection history, substance use history, beliefs around mask efficacy, treatment/prevention history, vaccine knowledge/attitudes, prior contact by contact tracer, experiences of racism, housing status, food insecurity, employment, experience of violence, workplace resources, PPE availability, and known COVID-19 contact.

Analytic overview. Two types of analyses will be performed.

The first will focus on the likelihood that a participant's network members are referred for testing. This will be modeled using logistic regression, with each network member treated as an observation (tested versus not). A three-level hierarchical model will be used, with random effects at the level of the study participant (level two) and the recruitment cluster (level three, all participants referred by the same index participant).⁴³ We shall also consider adding site as a fourth level to permit us to estimate between-site variability both in the outcomes and in the effectiveness of the interventions.

The second analysis will focus on the total number of individuals referred by a participant for testing, including both network members and additional referrals not initially named as part of the participant's network. The total number of referrals will be modeled using negative binomial regression.⁴⁴ A random effect at the level of the recruitment cluster will again be included to capture potential within-cluster correlation in the number of referrals. To ensure correct inferences even in cases where our models do not fully capture the within-cluster correlation in the data, we shall use the clustered version of the robust (i.e., sandwich) variance estimator throughout.⁴⁵

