Primary outcome analysis (overall comparison of SNS vs. SNS + messaging). The primary outcome analysis will compare the likelihood of testing among network members and the total number of referrals tested between those assigned to SNS and those assigned to SNS plus messaging. Our initial analysis will not adjust for covariates, relying instead on the randomization to justify the comparison. We shall then incorporate covariates—measured at both the level of the network member (e.g., member characteristics and the nature of the relationship to the participant) and of the participant—to improve the precision of our estimates and to identify demographic and social characteristics associated with differences in referral yield. In addition, we shall consider interactions between intervention group (SNS vs. SNS + messaging) and participant characteristics to determine whether messaging is more effective in certain groups than others. Since we shall consider several possible interactions, we shall use partial pooling within a Bayesian estimation framework⁴⁶ to avoid bias and address the issue of multiple comparisons.

We will compare the probability of participants being vaccinated in the SNS vs. SNS + messaging arm using logistic regression with each participant treated as an observation (vaccinated vs. not). This will be modeled with a three-level hierarchical model with random effects at the level of the recruitment cluster and study site. We will also consider adjustments for time trends in vaccine availability and participant eligibility.

Secondary outcome analyses: We shall use negative binomial regression to compare the average number of referrals tested per index client between those recruited to C3 and assigned to the SNS condition and a comparison group of clients at the same sites receiving standard contact tracing only. This analysis will be performed first using only those contact tracing clients who visited the sites on a day randomized to no C3 recruitment, since these individuals should, on average, be similar to those recruited into the study. A subsequent analysis will be performed using a larger set of non-study clients to increase precision; this will use covariates capturing demographic and other client characteristics to adjust for potential differences between the C3 SNS group and the non-study comparison group. Analyses will use generalized linear mixed models similar to those described above, as appropriate.

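### The first contact-tracing comparison rests on randomised days, but no planned model level or variance cluster contains the day, so its interval may be too narrow

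*Combined protocol and SAP*

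**What the plan says.** All references are to the combined protocol and SAP.

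- **Secondary outcome analyses, outcome and model.** The plan reads "We shall use negative binomial regression to compare the average number of referrals tested per index client between those recruited to C3" and assigned to SNS, and clients at the same sites who received contact tracing only.
- **Secondary outcome analyses, first comparison group.** The first analysis is made "using only those contact tracing clients who visited the sites on a day randomized to no C3 recruitment", on the argument that these people should on average resemble those recruited.
- **Secondary outcome analyses, model structure.** This is given by reference only: "Analyses will use generalized linear mixed models similar to those described above, as appropriate".
- **Analytic overview, count model.** "A random effect at the level of the recruitment cluster will again be included to capture potential within-cluster correlation in the number of referrals". A recruitment cluster is defined as "level three, all participants referred by the same index participant".
- **Analytic overview, variance.** "we shall use the clustered version of the robust (i.e., sandwich) variance estimator throughout", as protection where the models miss within-cluster correlation.
- **Site.** In the Analytic overview it is optional for the network-member model: "We shall also consider adding site as a fourth level". In the vaccination model (Primary outcome analysis) it is a definite random effect.
- **Study Visit Procedures, Randomization.** "Randomization will be performed at the participant level". This is the only allocation procedure described. How days were randomised is not set out.

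**The concern.** When comparability is drawn from randomising days, the day is the unit that carries the chance variation between the groups. A no-recruitment day supplies only contact-tracing clients to this comparison. To the extent that SNS index clients come from recruitment days, whatever the clients of one day share stays within one group and does not cancel. The SNS versus SNS+messaging contrast is different, because individuals are randomised there.

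The protections in the plan do not reach this correlation. With one record per index client, each C3 index is alone in its recruitment cluster, and contact-tracing clients have no recruitment cluster. The clustered sandwich then reduces to a client-level robust error. A site effect does not absorb variation between days within a site.

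At stake is the stated hypothesis that SNS strategies yield more people tested per index than contact tracing. If the standard error is understated, a chance difference between the two sets of days could be read as an SNS effect.

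**Working it through.** **No figure to reproduce.** Power calculations covers only SNS versus SNS+messaging and its interaction. For the contact-tracing comparison the documents give no sample size, power, number of days, clients per day or day ICC. The ICCs given (0.46 within a participant's network, 0.37 within a recruitment cluster) concern other groupings.

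**Inputs from the documents.** There are 300 index seeds with equal allocation, so about 300/2 = 150 SNS index clients. The negative binomial size implied by the power section's mean 4 and SD 2.8 is 4²/(2.8² − 4) = 16/3.84 = 4.17.

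**Assumed.** Clients per day per group m = 2 to 20; day ICC ρ = 0.01 to 0.10.

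**Step 1, closed form.** If the day is ignored, the true variance exceeds the reported one by VIF = 1 + (m − 1)ρ. The true SE is √VIF times the reported SE, and the true two-sided level is 2[1 − Φ(1.96/√VIF)].

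- m = 2, ρ = 0.01: VIF = 1.01, √VIF = 1.005, level 0.051.
- m = 10, ρ = 0.05: VIF = 1.45, √VIF = 1.204, level 0.104.
- m = 20, ρ = 0.10: VIF = 2.90, √VIF = 1.703, level 0.250.

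| Clients per day | ρ = 0.01 | ρ = 0.05 | ρ = 0.10 |
|---|---|---|---|
| 2 | 0.051 | 0.056 | 0.062 |
| 5 | 0.055 | 0.074 | 0.098 |
| 10 | 0.060 | 0.104 | 0.155 |
| 20 | 0.072 | 0.160 | 0.250 |

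The reported SE is thus 0.5% (1 − 1/1.005) to 41% (1 − 1/1.703) too small. With m = 1 or ρ = 0, VIF = 1 and nothing is lost.

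**Step 2, simulation with no true difference.** Negative binomial counts, 150 versus 150 clients, assumed mean 1.8, size 4.17, lognormal day effect, 1,500 runs. Entries are rejection rates in percent, client-level sandwich / day-clustered sandwich, without small-sample correction. Monte Carlo SE is about √(0.05 × 0.95/1500) = 0.6 points.

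| Clients per day | ρ = 0 | ρ about 0.03 | ρ about 0.10 |
|---|---|---|---|
| 2 | 5.5 / 6.1 | 6.4 / 6.3 | 5.9 / 5.1 |
| 5 | 5.4 / 5.8 | 6.7 / 5.5 | 9.4 / 5.1 |
| 10 | 5.2 / 6.4 | 8.5 / 6.7 | 16.9 / 6.9 |

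The simulation agrees with the formula. Clustering on day removes most of the inflation. The remainder at 10 per day (150/10 = 15 days per group) is why a small-sample correction is needed.

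**Step 3, plausibility of the upper end.** Over eight sites, 150 SNS index clients average 150/8 = about 19 per site. Twenty per day in the SNS group would therefore mean roughly a site's whole SNS index group on one day, or days shared across sites. For contact-tracing clients no daily number is given, so the upper end cannot be excluded there.

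**The case against.** The strongest reply is that the plan's wording allows model terms to be added where they fit, and that the harm is unquantified. SNS index clients may be spread thinly over many days; at 2 per day the true level is only 0.051 to 0.062. The outcome also accrues after the index visit, since network members may attend up to two weeks later. Conditions on the visit day itself may therefore matter little, and outbreak level may be shared by neighbouring recruitment and no-recruitment days. The analysis is secondary, has no stated power or decision rule, and is followed by a covariate-adjusted one.

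Most of this stands as a limit on size. It does not answer the omission: permission to add a term is not a plan to add it, and the variance clustering that is planned does not link same-day clients.

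A reader might also infer more than the documents support:

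- **That the interval is certainly too narrow.** This depends on two quantities that the documents do not give.
- **That the site-day is the randomised unit.** The text speaks of a day at the sites and does not say whether days were allocated per site or in common.
- **That site mix biases the ratio.** Comparison clients come from the same sites, the models referred to can include site, and no calculation here shows such a shift.
- **That day randomisation makes the groups comparable.** Seeds must also be eligible and consent, and may enter through flyers, social media or earlier studies (Recruitment; Inclusion and exclusion criteria).

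**Conclusion.** The point holds in conditional form. The first contact-tracing comparison draws on randomised days, and no named model level or variance cluster contains the day. Where same-day outcomes are positively correlated and days hold several clients, its interval is too narrow. The true level runs from about 0.051 to 0.25 over the assumed range, which the documents neither confirm nor exclude. The closed form assumes equal clients per day in both groups, and the simulation uses client-level and day-clustered sandwich errors rather than a fitted mixed model. This is worth correcting because a better variance is available from data that the analysis already needs. It concerns one secondary comparison only and does not touch the primary SNS versus SNS+messaging analysis.

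**What to change.** In Secondary outcome analyses:

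1. State the day unit that was randomised: per site, or common to all sites.
2. For the first contact-tracing comparison, cluster the sandwich variance on that unit in both groups (site-day if per site, calendar day if common) instead of on recruitment cluster, or add it as a random effect. Use a small-sample correction based on the number of day units.
3. Include site as a stratum.
4. Do not describe the SNS group as purely day-randomised. Say that eligibility, consent and other entry routes also select it, and that day clustering does not remove this selection.

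The cost is SAP wording and a somewhat wider interval. Visit dates must already be known to identify clients seen on no-recruitment days.

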University of Chicago will provide pre-programmed tablets to all study sites. These tablets have been programmed by the Research Computing Group within the Department of Public Health Sciences (leadership [name]) at the University of Chicago to ensure data protection and enable data transfer. All data collection will be conducted electronically via tablets and data will be uploaded into databases hosted by University of Chicago. These are similar procedures as have been developed with [name] for NIDA's Methodology and Advanced Analytics Research Center (PI [name]).

The University of Chicago BSD IRB will act as IRB of Record for all sites, except Indiana University (due to their enrollment of juvenile CJI populations) who will use their own institutional IRB.

METHODS

AIM: Test intervention efficacy (numbers tested – COVID-19 test results will be collected as study data; numbers vaccinated – COVID-19 vaccine records will be collected as part of the study) and community factors that may moderate efficacy. Secondary analysis to compare numbers tested in SNS strategies and COVID-19 contact and determine whether COVID-19 status within social networks impacts the referral process.

We hypothesize that participants randomized to receive SNS+ (SNS+COVID-19 messaging) will be more likely to have their network members successfully tested and vaccinated (study participants will be given COVID-19 vaccine information and contact information to vaccination sites in their community. Vaccination will depend on the network members' tier/health department eligibility for vaccination). We also hypothesize that both SNS and SNS+ will generate more people tested per index as compared to COVID-19 contact tracing. Finally, we anticipate that there may be differential intervention effects across sites, by CJI status, prior COVID-19 testing history, race/ethnicity, and network composition, and will formally evaluate these differences as part of analyses.

Recruitment of Index and Network Member study participants.

We will enroll index seeds (12% of sample) ages 18 and over who are CJI or low-income Latinx across eight collaborative sites. Index clients and their social network referrals will be recruited by local Research Assistants (RAs) embedded within community-based agencies and community health care settings that provide a number of in person and remote social and care services, including community COVID-19 testing.

Recruitment activities may include:

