Power calculations: In order to estimate our power, we performed the following simulation. We assumed that index participants generate network members according to a negative binomial distribution with mean 4 and SD 2.8 (to match the study design, networks larger than 6 were truncated). Each network member comes in for testing with a probability determined by the group to which they are assigned, and we conservatively assume intraclass correlations of 0.46 within a participant's network and 0.37 within a recruitment cluster. If we assume that the overall likelihood of testing among network members is 0.44 among the SNS group and 0.52 among the SNS plus messaging group, then an overall sample size of 2,400 participants will provide approximately 87% power to detect the difference at the 0.05 level (twosided). We shall have approximately 80% power to detect an interaction between the intervention and a binary participant characteristic (Groups A and B) such that the overall probability of testing for those receiving SNS only (both A and B) is 0.44, the probability of testing for those in Group A receiving SNS plus messaging is 0.50, and the probability of testing for those in Group B receiving SNS plus messaging is 0.63 (i.e., messaging is more effective among Group B).

Attrition and missing data: All participants enrolled in the study will be included in our analyses; since the primary outcomes will be measured based on referrals coming in to get tested which does not require additional participation by the participant, we anticipate very little missing outcome data (referrals who come in for testing and decline to identify the person who referred them will not be counted). Any missing data will be addressed using multiple imputation⁴⁷ or by using a fully Bayesian approach to estimate the model⁴⁸ (in which missing data are essentially treated as additional unknown parameters).

POTENTIAL RISKS AND BENEFITS TO SUBJECTS

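### The stated 80% interaction power does not fit the stated 87% main-effect power: at two-sided 0.05 with equal groups it would be about 71–73%, and the interaction's alpha and A:B split are not given

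*Combined protocol and SAP*

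**What the plan says.** Under Power calculations, the main comparison assumes that "the overall likelihood of testing among network members is 0.44 among the SNS group and 0.52 among the SNS plus messaging group", and the section concludes that "an overall sample size of 2,400 participants will provide approximately 87% power to detect the difference at the 0.05 level (twosided"). The next sentence says "We shall have approximately 80% power to detect an interaction between the intervention and a binary participant characteristic (Groups A and B"). Its scenario is 0.44 under SNS only in both groups, and 0.50 (Group A) and 0.63 (Group B) under SNS plus messaging. No level, sidedness or A:B split is attached to it.

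Three other places bear on it:

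- **Study Visit Procedures, Randomization:** assignment is 1:1. "Randomization will be performed at the participant level, meaning that in general, participants within a recruitment cluster will be assigned to different groups".
- **Methods, Aim:** effects may differ by site, CJI status, testing history, race/ethnicity and network composition, and the investigators "will formally evaluate these differences as part of analyses".
- **Primary outcome analysis:** because several interactions will be considered, "we shall use partial pooling within a Bayesian estimation framework".

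**The concern.** An interaction contrast between two equal subgroups has about twice the standard error of the overall effect. Here the interaction (0.13) is only 1.6 times the main effect (0.08), so its power should fall well below 87%. A fall to only 80% looks too small.

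This sentence is the plan's only power statement for differential effects, which the Aim says will be formally evaluated. A reader who carries the 0.05 level over from the preceding sentence would credit the trial with 7–9 points more power than its companion figure supports. The overstatement would be larger for an uncommon characteristic.

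**Working it through.** **Inputs.** From Power calculations: 87% main-effect power at two-sided 0.05; 0.44 versus 0.52; interaction cells 0.44, 0.44, 0.50 and 0.63; stated interaction power 80%. From Randomization: 1:1, by participant. Assumed, because not stated: two-sided 0.05 for the interaction, and Group B share q = 0.5, with other values shown.

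**Step 1. Standard error implied by 87%.**
z(0.975) + z(0.87) = 1.960 + 1.126 = 3.086.
- Risk difference: SE = 0.08 / 3.086 = 0.0259.
- Log odds: logit(0.52) − logit(0.44) = 0.3212; SE = 0.3212 / 3.086 = 0.1041.

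This takes the 87% as given. It cannot be rebuilt from the text, because the number of clusters, the ICC scale, the contributing waves and the simulated analysis model are not stated.

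**Step 2. Interaction standard error.** SE(interaction) = SE(main) / √(q(1−q)). At q = 0.5 the factor is 2: 0.0518 (risk difference) or 0.2081 (log odds).

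**Step 3. Interaction contrast.**
- Risk difference: (0.63 − 0.44) − (0.50 − 0.44) = 0.13.
- Log odds: logit(0.63) − logit(0.50) = 0.532.

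**Step 4. Power at two-sided 0.05, q = 0.5.** Power = Φ(contrast/SE − 1.960).
- Risk difference: 0.13 / 0.0518 = 2.51; power 70.8%.
- Log odds: 0.532 / 0.2081 = 2.56; power 72.5%.
- Using the variances of the four cells instead of exact doubling: 71.5% and 71.7%.
- Reading 87% as anything from 86.5% to 87.5%: 70.2% to 73.1%.

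**Step 5. Other assumptions.**

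| Group B share | Level (two-sided) | Power: risk difference / log odds |
|---|---|---|
| 50% | 0.05 | 70.8% / 72.5% |
| 40% | 0.05 | 69.0% / 70.7% |
| 30% | 0.05 | 63.2% / 64.9% |
| 20% | 0.05 | 51.8% / 53.4% |
| 50% | 0.10 | 80.6% / 81.9% |

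Equal groups are at or near the most favourable split, so no split reaches 80% at 0.05.

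**Step 6. In reverse.** 80% power at two-sided 0.05 needs z = 1.960 + 0.842 = 2.802.
- The interaction-to-main SE ratio would have to be 0.13 / (2.802 × 0.0259) = 1.79, or 1.83 on the log-odds scale, instead of 2.
- With the ratio at 2, main-effect power would have to be 92–93%.
- With 87% kept, the Group B probability would have to be about 0.642–0.645.

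**Step 7. Does clustering change the factor of 2?** Simulations used 300 clusters, the plan's network-size distribution (capped at 6) and its two ICCs in nested or additive form, with 4,000 replicates and a cluster-robust test. The number of referring participants per cluster was an assumption, tuned to give 87%.
- Four 50:50 runs, with A/B membership independent or shared within cluster: main-effect power 86.7–87.8%, SE ratio 1.98–2.02, interaction power 71.2–72.7% at 0.05 and 81.4–81.7% at 0.10.
- Two 30:70 runs: main-effect power 87.2–87.4%, SE ratio 2.17–2.19, interaction power 64.7–65.2% at 0.05.

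Separate untuned simulations (1,500 replicates, cluster-robust logistic regression, 50:50) gave main-effect and interaction powers at 0.05 of 83–85% and 60–68% when only index and first-degree participants contributed outcomes. When all 2,400 contributed, they were about 98% and 89–94%. Neither structure gave 87% together with 80%.

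**The case against.** The algebra is hard to dispute, but four objections deserve an answer.

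- **Unstated alpha.** The interaction sentence names no level, and two-sided 0.10 with equal groups gives 80.6–81.9%. This may be an omitted assumption and not an arithmetic error. That stands as a possible explanation, but the plan would then have changed alpha between adjacent sentences without saying so.
- **Monte Carlo error.** The replicate count is not given. If it were 200 and true main-effect power were 90%, interaction power would be 75–77%, with Monte Carlo standard errors of about 2 and 3 points. Observing 87% and 80% would then be about 1.4 and 1.1–1.7 standard errors off. This needs a very small simulation and errors in opposite directions in both figures; at 500 replicates it is much less plausible, and at 1,000 it fails.
- **The factor of 2 is not an identity.** It depends on the set-up: a rough check with cluster-level assignment and a participant-level characteristic gave ratios of 0.9–1.45. That is not the design described. Under participant-level assignment the ratio stayed near 2. The tuned simulations support this ratio, but they cannot show which stated power is off.
- **Little depends on it.** The interactions are to be estimated with Bayesian partial pooling, so neither 80% nor 72% describes the planned analysis, and the unequal splits are illustrations. This limits the impact but does not reconcile the two figures.

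**Conclusion.** The concern holds. At two-sided 0.05, 87% for the main effect implies about 71–73% for the interaction with equal groups, against the 80% stated: a gap of 7–9 points, growing as the groups become unequal. This rests on the 0.05 level carrying over, on 1:1 participant-level randomization as described, and on the same analysis model for both tests. It does not depend on rebuilding the 87%.

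The documents do not show whether the 87%, the 80% or an unstated level is responsible. The impact is modest, because the primary comparison, sample size and planned analysis are unaffected. The statement should still be corrected or completed, since nothing else in the plan supports the power of the differential-effect analyses.

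**What to change.** State the alpha, sidedness and A:B split used for the interaction, and reconcile the two powers from the simulation output. Then, according to what that output shows:

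- **Level was two-sided 0.05 and 87% stands:** restate the interaction power as about 71–73% for equal groups, with lower figures for unequal groups; or keep 80% and restate the detectable Group B probability as about 0.642–0.645.
- **87% is the figure that is off:** correct that one.
- **Level was two-sided 0.10:** say so.

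In every case, note that the figure describes a single unpooled test (if that is what was simulated), not the planned partial-pooling analysis. The cost is one or two sentences and possibly a slightly less favourable stated power.
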